9. SAFETY ASSESSMENT

9.1 DEFINITION OF AE

An adverse event (AE) is defined as any unfavorable and unintended sign including an abnormal laboratory finding, symptom or disease associated with the use of a medical treatment or procedure, regardless of whether it is considered related to the medical treatment or procedure, that occurs during the course of the study.

9.2 DEFINITION OF SAE

A **serious adverse event** (SAE) is any adverse experience occurring during the course of the study or during planned follow-up. Any adverse event that meets **any of the following** criteria MUST be reported to the CPHS:

- results in death;
- is life-threatening (places the patient at immediate risk of death from the experience as it occurred);
- results in a persistent or significant disability/incapacity (substantial disruption of one's ability to carry out normal life functions);
- results in medical or surgical intervention;
- results in OR prolongs an existing inpatient hospitalization (even if the hospitalization is a precautionary measure for observation);
- is a congenital anomaly/birth defect in offspring of subjects taking the product regardless of time to diagnosis;
- is a cancer;
- is the result of an overdose, whether intentional or accidental, including a breach of protocol;
- is medically unexpected, regardless of severity

9.3. DEFINITION OF UNANTICIPATED PROBLEMS

Unanticipated problems are not synonymous with "adverse events". Unanticipated problems refer to untoward events involving any aspect of a research study, not just subjects, and can occur in clinical and non-clinical research. Some examples of unanticipated problems include:

- An investigator loses a laptop that contains confidential information about participants.
- A principal investigator is charged with a felony.
- A lab reports that blood studies performed the previous week were in error.
- A man physically abuses his wife because she agreed to take part in a research study without his permission.
- Subjects in a group counseling session become unexpectedly violent.

All unanticipated problems will be reported to CPHS via iRIS.

9.4 AE REPORTING GUIDE

Reporting of adverse events, serious and/or unexpected, will follow the CPHS guidelines found at: <http://www.uth.tmc.edu/orsc/guidelines/adv.html>

Cognitive-enhancing DA Medications for Cocaine Dependence

NCT01393457

Version Date: 09/02/2011

STATISTICAL ANALYSIS PLAN (SAP)

Data will be entered by research assistants into an existing, relational database (i.e. Microsoft Access). Data integrity will be maintained by restricting allowable input values on standardized Access entry forms. Double entry of a random subset of 10% of the observations will be used to identify problematic data entry issues. Preliminary data analyses evaluating group differences on demographic and baseline variables will use contingency tables with chi-square testing, ANOVA's, and examination of correlations between baseline variables and specified outcomes. Baseline or demographic variables, on which group differences are detected and which are correlated with outcomes, meet the definition of confounders and will result in two sets of analyses: one in which the relevant variable is included as a covariate and one in which it is not. This will permit determination of the degree to which any group differences might confound conclusions regarding treatment.

Broadly, the data analytic strategy will use generalized linear modeling and mixed effects models. Longitudinal analyses will be conducted using generalized linear mixed modeling (Proc GLIMMIX; SAS 9.2) for both continuous and discrete outcomes. Count, dichotomous and time to event data will be evaluated using Poisson (Proc GENMOD; SAS 9.2), logistic (Proc GENMOD; SAS 9.2), and proportional hazards regression (Proc PHREG; SAS 9.2) respectively. Distributional assumptions will be evaluated via inspection of residual plots and, where possible, by formal statistical tests. Violation of assumptions will be addressed, depending upon statistical technique, through the use of transformations, robust estimators, scaling coefficients, and stratification. Sample size approximations are obtained through empirical data simulation using SAS v.9.2.

PRIMARY HYPOTHESIS TESTING: To evaluate the efficacy of combination levodopa/carbidopa-ropinirole therapy in treatment of cocaine dependence. H1. The combination of levodopa/carbidopa and ropinirole will reduce cocaine use and increase treatment retention. H2. There will be a dose-response relationship such that
 $[\text{levodopa}/\text{carbidopa} + 4 \text{ mg/d ropinirole}] > [\text{levodopa}/\text{carbidopa} + 2 \text{ mg/d ropinirole}] > [\text{levodopa}/\text{carbidopa} + \text{placebo}] > [\text{placebo} + \text{placebo}]$. H1 will test for differential change over time as a function of treatment. H2 will test the ordinal relations of treatment effects as a follow-up analysis. As defined above (see Sect. B.3.2.5.ii) cocaine use will be measured by urine benzoylecgonine and by the SPRHK1 approach. Generalized linear mixed models will evaluate the probability of cocaine use as a function of time, treatment and their interaction. Logistic regression will evaluate retention, defined by completion of 12 weeks of treatment, as function of intervention condition. Proportional hazards regression will evaluate time to drop-out as a function of treatment. If differential attrition raises concerns regarding non-ignorable missingness, evaluation of cocaine use will implement pattern-mixture modeling. To evaluate the relative efficacy of the treatment conditions we will follow up the omnibus test with ordinal contrasts.

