7.2 STUDY SPECIFIC

7.2.1 ENROLLMENT/RANDOMIZATION

An urn randomization procedure will be used to assign subjects to one of the four treatment groups. This procedure will balance groups on important pretreatment characteristics that may influence measures of cognitive performance and/or treatment outcome. The variables will include (1) severity of cocaine dependence, based on days using cocaine in past 30; (2) baseline (trait) impulsivity score, based on the Barratt Impulsiveness Scale (BIS). The BIS was chosen as a variable for the urn randomization because it has norms for high and low impulsivity in cocaine users based on previous studies and has been predictive of treatment retention.

Treatment assignment will be concealed to all clinical and research staff, including the investigators. Only the study pharmacist who dispenses the study medication will be unblinded to participants' assigned condition.

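### The SAP's only stated route to covariate adjustment is a detected baseline difference; pre-specifying the two urn variables may raise power for retention and drop-out, with little or no gain for the time-by-treatment test

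*SAP*

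**What the plan says.** **Covariate rule (SAP, preliminary analyses).** Groups are compared at baseline by chi-square tests and ANOVA, and baseline variables are correlated with outcomes. Then: "Baseline or demographic variables, on which group differences are detected and which are correlated with outcomes, meet the definition of confounders". Such a variable leads to two sets of analyses, with and without it. No significance level is given for the baseline tests, and neither set is named primary.

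**Outcome models (SAP, primary hypothesis testing).** No covariate appears in any of them:
- Cocaine use: "Generalized linear mixed models will evaluate the probability of cocaine use as a function of time, treatment and their interaction".
- Retention: "Logistic regression will evaluate retention, defined by completion of 12 weeks of treatment, as function of intervention condition".
- Drop-out: "Proportional hazards regression will evaluate time to drop-out as a function of treatment".

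**Hypotheses.** H1 reads "The combination of levodopa/carbidopa and ropinirole will reduce cocaine use and increase treatment retention", and "H1 will test for differential change over time as a function of treatment". For the dose ordering, "H2 will test the ordinal relations of treatment effects as a follow-up analysis"; the SAP does not say whether those contrasts are on levels or on slopes.

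**Randomisation (Protocol 7.2.1).** The urn balances on variables thought able to affect cognitive performance or outcome: "The variables will include (1) severity of cocaine dependence, based on days using cocaine in past 30; (2) baseline (trait) impulsivity score". The section adds that BIS has predicted retention in earlier work.

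**The concern.** The protocol singles out two variables as potentially prognostic, collects them before randomisation and balances on them. The SAP then lets them into a model only if balance appears to have failed. That is the wrong trigger for a prognostic covariate. The reason to include one is that it explains outcome variation, and this holds however well the arms are balanced. Successful balancing makes omission more likely still.

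What is at stake is efficiency. Retention is where the case is best supported, because it is the outcome for which the protocol calls BIS predictive. The SAP places retention within H1 under its primary hypothesis heading, although the protocol abstract lists time in study as secondary. There is also a loose end: when a variable is flagged, two results exist and the SAP does not say which one counts.

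**Working it through.** **1. What can be reproduced.** The protocol's 200 patients in four equal arms gives 200/4 = 50 per arm, and 40 months × 5 per month = 200. The SAP says that sample size came from simulation but gives no alpha, power, effect size or variance, so the power behind 200 cannot be re-derived. Everything below uses 200 patients in four arms; every other input is assumed.

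**2. How often both variables are left out.** Under simple randomisation each variable is flagged with probability equal to the test level. Neither is flagged with probability 0.95² = 0.9025 at 0.05, 0.90² = 0.81 at 0.10 and 0.80² = 0.64 at 0.20. Simulation gave 0.902, 0.809 and 0.648. With an urn on median splits (assumed; no cut-points are given), each is flagged in about 2.0% of trials at 0.05, so 0.98² = 0.960 (simulated 0.960–0.962). The ranges below run from the difference condition alone to both conditions (correlation with outcome at p<0.05, R² 5%).

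| Test level | Simple randomisation | Urn |
|---|---|---|
| 0.05 | 90–93% | 96–98% |
| 0.10 | 81–88% | 89–94% |
| 0.20 | 65–78% | 77–86% |

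Most of this comes from the rule itself; the urn adds a few points at 0.05.

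**3. What inclusion would change.** R² is the share of latent outcome variance (between-person variance in the GLMM) that the two variables explain together. For logistic regression R² = 2b²/(2b² + π²/3): b = 0.29, 0.43 and 0.64 per SD give 5%, 10% and 20%. For proportional hazards R² = 2b²/(2b² + π²/6): b = 0.21, 0.30 and 0.45 give the same. The GLMM is a binary random-intercept model over 10 weeks with three urines per week. Power (%) is shown unadjusted → adjusted, with ordered treatment effects.

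| Test | R² 5% | R² 10% | R² 20% |
|---|---|---|---|
| Retention, omnibus | 61.4→63.3 | 57.7→61.9 | 50.0→58.1 |
| Retention, trend | 78.7→80.2 | 76.1→78.3 | 69.5→74.8 |
| Drop-out, omnibus | 54.6→57.5 | 52.1→57.8 | 46.3→58.6 |
| Drop-out, trend | 72.3→74.6 | 70.8→75.5 | 65.1→75.8 |
| GLMM level, omnibus | 52.6→55.0 | 52.4→56.2 | 52.1→63.4 |
| GLMM level, trend | 68.6→71.2 | 69.1→73.1 | 69.8→77.9 |
| GLMM time × treatment | 41.4→41.6 | 42.0→41.9 | 41.3→41.2 |

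With one outcome per week the GLMM pattern is the same, and time × treatment moves by at most 0.7 point (37.2→37.9).

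**4. Where the gain comes from.** In the GLMM, the SE of a level contrast falls (unadjusted/adjusted ratio 1.02, 1.04–1.05 and 1.09–1.10). In the logistic model the SE rises (0.422→0.436 at 5%, 0.418→0.462 at 20%), and in the hazards model it rises slightly (0.291→0.293, 0.289→0.291, 0.287→0.290). Power still improves there because the conditional coefficient lies further from zero. The slope contrast rests on within-person change, from which a time-constant main effect drops out.

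**5. If the variables do not predict outcome (R² = 0).** Power changes by −0.3 to +0.5 point: retention 64.5→64.2 and 55.5→56.0, drop-out 56.6→56.8, GLMM level 52.9→52.9 (omnibus) and 69.8→70.1 (trend).

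**6. False positives.** GLMM level omnibus under the null: 5.5%→5.9% (R² 5%) and 4.8%→5.7% (R² 20%). The Monte Carlo SE is √(0.05 × 0.95/1600) = 0.5 point, so the highest rate is about 1.7 SE above 5%. Logistic omnibus null rates in a second simulation were 4.4→4.3, 5.0→4.1 and 4.5→4.0%. No null runs were made for the hazards model.

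**7. Second simulation, different assumed inputs (highest dose against placebo).** Retention power rose 81→82, 77→79 and 65→73% at covariate log odds ratios of 0.3, 0.5 and 0.8 per SD. Drop-out power rose 58→63 and 49→59% at log hazard ratios of 0.3 and 0.5. The time × treatment SE went from 0.359–0.360 to 0.355–0.359 with covariates explaining 10–50% of between-person variance.

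**The case against.** **The rule is a confounding check, not a ban.** This is fair. The SAP never says that covariates may enter only this way, and it cites a section (B.3.2.5.ii) that is not in the supplied text. A reader might infer that prognostic adjustment is forbidden; the documents do not say that. What stands is that no other route is stated and no model names a covariate. The missing section is cited for how cocaine use is measured, not for covariates.

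**The main cocaine-use test gains nothing.** Largely right. A reader might infer that H1's time-by-treatment test is losing power; for main effects it is not. A covariate-by-time term could help if the variable predicts slope. A linear analogue with assumed variances gives a slope SE of 0.0358 falling to 0.0347–0.0323 when 10–30% of slope variance is explained, but nothing in the documents supports such a figure.

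**Precision does not improve for retention and drop-out.** Correct for the SAP's own coefficients: the gain there is in power. Precision improves for GLMM level contrasts, which matters only if H2's ordinal contrasts are on levels.

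**The size is assumed.** Also correct. The protocol says only that these variables may matter. At R² 5% the gain is 1–3 points, and one pairwise logistic comparison went from 67.2% to 66.4%. The larger gains need R² near 20%, which no document supports.

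**Retention may be unusable as defined.** This stands as a condition. The SAP requires 12 weeks of treatment, the protocol abstract describes 10, and section 7.2.3 describes 9. The drop-out model does not use that definition.

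**Conclusion.** The point holds as a free improvement, with medium confidence. Under the stated rule both urn variables would be left out in roughly 90–98% of trials if detection means p<0.05, and somewhat less often at looser levels. If they are prognostic with R² of 5–20%, pre-specifying them adds about 1–8 points of power for logistic retention and 2–12 for drop-out. For GLMM level contrasts it adds about 2–11 points, if such contrasts are used. It adds essentially nothing for time × treatment when they enter as main effects. If they are not prognostic, no material loss was seen.

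A reader might conclude that omission biases the treatment effects or inflates false positives. Nothing supports that: allocation is randomised, and the simulated unadjusted null rates are close to 5%. The defect is possible lost efficiency, plus an unnamed primary analysis whenever a variable is flagged. All sizes rest on two independent, normally distributed covariates of equal effect, a median-split urn and assumed treatment effects; none of these is given in the documents.

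**What to change.** - Pre-specify days of cocaine use in the past 30 and BIS score as covariates in the GLMM, logistic and proportional hazards models, whatever the observed balance.
- Name that analysis primary and the unadjusted one a sensitivity analysis.
- Drop the detected-difference test as the trigger for adjustment.
- State that adjusted odds and hazard ratios are conditional on the covariates.
- Say whether H2's ordinal contrasts are on levels or slopes, and reconcile the 12-, 10- and 9-week treatment lengths before relying on the retention model.

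The covariate change costs SAP wording only. The urn already requires both variables at randomisation, so no new data, visits or patients are needed. The one consequence to declare is the move from marginal to conditional odds and hazard ratios.

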1. ABSTRACT/STUDY DIAGRAM

Most cocaine dependent patients suffer from deficits in cognitive function that, if left untreated, predict poor outcome.

Purpose: The present study investigates a pharmacotherapeutic intervention designed to improve cocaine treatment success by combining medications that act simultaneously on dopamine, the brain system that is critically associated with chronic cocaine use and cognitive functions. **Procedures:** Treatment with levodopa/carbidopa plus ropinirole (tested at two doses) will be compared to levodopa/carbidopa alone, and placebo. Measurement of performance on behavioral/cognitive measures of decision-making, behavioral inhibition, reward motivation, and attentional bias will be conducted at treatment entry and at repeated time points during the 10-week treatment. It is hypothesized that treatment with levodopa/carbidopa + ropinirole will produce superior outcomes in terms of reduced cocaine use and increased treatment retention and that these effects will occur indirectly via improved performance on observed cognitive mechanisms. **Course of Study:** Eligible cocaine dependent patients will be randomized equally to one of four medication conditions. Outpatient treatment will last 10 weeks and consist of thrice-weekly clinic visits. The behavioral therapy platform for this trial will consist of weekly cognitive behavioral therapy (CBT). The primary outcome measure will be weekly mean proportion of cocaine non-use days. Secondary endpoints will include abstinence rates during the last 2 weeks of treatment, time in study, and medication compliance. **Enrollment:** This project requires a final intent-to-treat sample size of 200 subjects. To obtain this sample, we expect to conduct phone screens on ~ 640 individuals, of whom 320 (50%) will qualify, enroll, and start intake. Of the 320 who start intake, we expect that 200 (~60%) will complete intake and be randomized into the ITT sample. Based on these projections and recruitment rates achieved during our previous levodopa studies, 40 months will be allotted to complete study enrollment (~ 5 new subjects/month).

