7.2.3 IN TREATMENT

During the 9-week treatment phase participants will be scheduled to attend three clinic visits per week (MWF). Activities conducted at these visits will include urine testing, administration of study medication, cognitive behavioral therapy, and prize-based CM for attendance. Brief (5-10 min) evaluations by the study nurse will be conducted weekly to address concerns related to side effects, concomitant medications, and general adherence to the medication regimen.

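### The SAP does not carry over the protocol's single primary outcome: it uses two unranked cocaine-use measures and places retention, a protocol secondary, inside primary H1

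*SAP*

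**What the plan says.** Protocol section 1 (Abstract/Study Diagram) gives one primary outcome: "The primary outcome measure will be weekly mean proportion of cocaine non-use days". It continues: "Secondary endpoints will include abstinence rates during the last 2 weeks of treatment, time in study, and medication compliance". The hypothesis in the same section is broader and expects "superior outcomes in terms of reduced cocaine use and increased treatment retention", but only the cocaine outcome is called primary.

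The SAP, under Primary Hypothesis Testing, states H1 as: "The combination of levodopa/carbidopa and ropinirole will reduce cocaine use and increase treatment retention". It says that H1 concerns differential change over time by treatment, and that "cocaine use will be measured by urine benzoylecgonine and by the SPRHK1 approach", with Sect. B.3.2.5.ii cited for the definition. It then lists three analyses:

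- a generalized linear mixed model for the probability of cocaine use, with time, treatment and their interaction;
- a logistic regression for retention, defined as completing 12 weeks;
- a proportional hazards regression for time to drop-out.

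An omnibus test is followed by ordinal contrasts across the four arms. The SAP does not mention non-use days, does not rank the two cocaine measures, and does not say which measure the omnibus test uses.

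**The concern.** A reader who starts from the protocol expects one confirmatory test, on non-use days. A reader who starts from the SAP finds a primary hypothesis with a cocaine part and a retention part, two measures for the first and two models for the second.

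The two cocaine measures may give different answers, and so may cocaine use and retention. If the choice of deciding measure is not fixed in writing beforehand, it can be influenced by the results. The same choice determines which omnibus result leads into the H2 dose-order contrasts. At stake are the error rate of the primary claim and whether that claim can be traced to the outcome the protocol declared.

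**Working it through.** **Step 1: set the two documents side by side.**

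| Item | Protocol, section 1 | SAP, Primary Hypothesis Testing |
|---|---|---|
| Primary cocaine outcome | Weekly proportion of non-use days | Not named; probability of cocaine use is modelled |
| Measure of cocaine use | Not specified there | Urine benzoylecgonine and SPRHK1, unranked |
| Rank of retention | Time in study is secondary | Part of primary H1 |
| Retention analyses | One endpoint, time in study | 12-week completion (logistic) and time to drop-out (proportional hazards) |
| Length of treatment | 10 weeks | Completion means 12 weeks |

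The first two rows may be resolved by Sect. B.3.2.5.ii. The row on retention's rank is a direct mismatch between the supplied texts. The last row is a second mismatch. Protocol section 7.2.3 adds a third duration, a 9-week treatment phase.

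**Step 2: identify the test that most naturally decides H1.** H1 is said to test differential change over time. Of the three listed analyses, only the cocaine-use mixed model has a time-by-treatment term. That term is therefore the natural candidate for the omnibus test. What remains open is the measure to which it is applied.

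**Step 3: size the consequence of leaving the measure open.** There is no plan figure to reproduce, because the documents give no significance level, sidedness or correlation between the measures. Assumptions: each measure is tested two-sided at 5%, there is no true effect, and significance on either measure suffices. Then

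P(at least one significant) = 0.05 + 0.05 − P(both significant).

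For a 1-df test, P(both) comes from the bivariate normal distribution:

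- correlation 0.5: 0.100 − 0.0093 = 0.0907
- correlation 0.8: 0.100 − 0.0219 = 0.0781
- correlation 0.9: 0.100 − 0.0296 = 0.0704
- correlation 0.95: 0.100 − 0.0354 = 0.0646

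A treatment-by-time test over four arms has 3 df if time is linear, which is also an assumption. Simulating two correlated 3-df chi-square tests (4 million draws per case) gives the last column.

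| Correlation of the two measures' tests | Either significant, 1 df | Either significant, 3 df |
|---|---|---|
| 0.5 | 9.1% | 9.2% |
| 0.8 | 7.8% | 8.0% |
| 0.9 | 7.0% | 7.2% |
| 0.95 | 6.5% | 6.6% |

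The range is about 6.5% to 9.2%; individual simulation runs at 0.95 went as low as 6.4%. The ceiling, for independent tests, is 1 − 0.95² = 9.75%. One named measure gives 5%.

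**The case against.** The strongest reply is that the plan is more complete than the supplied text. The SAP says that cocaine use has already been defined and cites a section for it. That section could rank the measures, or show that SPRHK1 is the rule that turns urine results into the protocol's outcome. In either case there is one deciding measure and no inflation. This stands. A reader might infer that the sponsor had no definition, or that the choice was bound to be made after the data were seen; the documents support neither.

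A second reply is that probability of use and proportion of non-use days are complements, so the model may already address the protocol's outcome. That is plausible, but the supplied text does not say how visit-level urine results become days. A reader might go further and argue that thrice-weekly urine cannot yield a proportion of days in a seven-day week. The protocol gives no denominator for that proportion, so this cannot be asserted.

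A third reply is that H1 joins its two parts with a conjunction and that the protocol has already ranked time in study as secondary. Read literally, a result on one part alone does not meet H1. This also largely stands. It rules out a further tempting inference, that success on any of the four analyses (two cocaine measures, two retention models) would do, with an error rate of up to 1 − 0.95⁴ = 18.5%. But the reply leans on the two documents at once, and they disagree: the protocol makes retention secondary, while H1 makes it a condition of the primary claim.

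**Conclusion.** The point holds as a mismatch between the documents. The supplied SAP does not name the protocol's primary outcome, does not say which of two cocaine measures enters the model that tests H1, and gives retention a higher rank than the protocol does. The first two gaps may be closed by Sect. B.3.2.5.ii; the last is visible in the supplied text.

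If either cocaine measure may carry the claim, the false-positive risk is about 6.5% to 9.2% instead of 5%. That rests on an assumed 5% per test and assumed correlations of 0.95 to 0.5. It describes one permissive reading and is not evidence that the trial's error rate is inflated. If one measure was fixed beforehand, the cocaine claim stays at 5%.

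This is an inexpensive improvement to the SAP and does not invalidate the trial. Confidence is medium because of the unseen section.

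**What to change.** Amend the SAP before unblinding as follows.

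- Name the protocol's primary outcome as the outcome of one primary PROC GLIMMIX model, using one named measure consistent with Sect. B.3.2.5.ii, and restate that definition in the SAP. Make the other cocaine measure a sensitivity analysis.
- State that the treatment-by-time test in this model is the omnibus test that precedes the H2 ordinal contrasts.
- Split H1. Cocaine use is the primary part; retention, with both its analyses, becomes secondary and is reported as a separate claim, in line with protocol section 1.
- Reconcile the 12-week completion definition with the 10-week treatment in protocol section 1 and the 9-week phase in section 7.2.3.

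The change is to wording and needs no more patients. Whether the chosen measure calls for data beyond those already collected cannot be confirmed without the cited section. The real price is that neither retention nor the second cocaine measure can then support the primary claim on its own.

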6.5 NON MEDICATION INTERVENTIONS

Cognitive Behavioral Therapy (CBT). Participants will receive individual CBT in 50-minute weekly sessions. Including CBT will allow us to replicate the behavioral therapy condition that proved most efficacious when used previously in our levodopa and citalopram trials. Cognitive-behavioral therapy is based on the model of relapse proposed by Marlatt and Gordon. The model regards coping skills training as the key component for avoiding drug use and preventing relapse. Skills training techniques include (1) self-monitoring and functional analysis of situational factors associated with craving or drug use; (2) learning alternative non-drug responses for handling high risk situations; and (3) general lifestyle modifications (e.g., increasing pleasant drug-free events, anger management, interpersonal skills, general problem-solving). An unpublished treatment manual written by [name] (PI) and implemented in several completed studies, closely parallels the treatment content found in other published CBT manuals. All CBT sessions will be audio-taped for adherence and competence ratings using recommended procedures done in all our treatment studies. Weekly supervision will be held by a designated clinical supervisor who will provide feedback to keep CBT delivery consistent and prevent drift.

Prize-based attendance CM (Contingency Management). During Treatment, for each visit attended, subjects will earn a draw from the attendance voucher “fishbowl”. The fishbowl has 500 slips in it. Many of the slips have a value of \$1, some have a value of \$25, one slip is worth \$100, and half of the slips just say “Good Job”. Subjects will earn 5 bonus draws for each week in which all 3 visits in a week (that is, Monday, Wednesday, and Friday) are attended. Vouchers for the \$25 and \$100 value slips will be given in the form of a gift card. For the \$1 slips, \$1 in cash or a voucher will be given.

The schedule of fishbowl draws for attendance and compliance is shown in Table 1 below.

Table 1. Draw Schedule

Week	1			2			3			4			5		
Visit	1	2	3	4	5	6	7	8	9	10	11	12	13	14	15
Draws	1	1	1	2	2	2	3	3	3	4	4	4	5	5	5
Bonus			5			5			5			5			5
Total Draws	1	1	6	2	2	7	3	3	8	4	4	9	5	5	10
Week	6			7			8			9			10		
Visit	16	17	18	19	20	21	22	23	24	25	26	27	28	29	30
Draws	6	6	6	7	7	7	8	8	8	9	9	9			
Bonus			5			5			5			5			
Total Draws	6	6	11	7	7	12	8	8	13	9	9	14			
Week	11			12			13			Total: 180 Draws					

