Visit	31	32	33	34	35	36	37	38	39	Total: 180 Draws					
Draws										Total: 180 Draws					
Bonus										Total: 180 Draws					
Total Draws										Total: 180 Draws					

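### The SAP defines retention as completing 12 weeks of treatment, but the protocol schedules at most 10, so the logistic completer analysis under H1 cannot be estimated as written

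*SAP*

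**What the plan says.** The SAP, under Primary Hypothesis Testing, makes retention part of its first hypothesis: "H1. The combination of levodopa/carbidopa and ropinirole will reduce cocaine use and increase treatment retention". It plans two analyses of retention. One is binary: "Logistic regression will evaluate retention, defined by completion of 12 weeks of treatment, as function of intervention condition". The other is a time-to-event analysis: "Proportional hazards regression will evaluate time to drop-out as a function of treatment".

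The protocol describes the length of treatment in several places:

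- **Section 1 (abstract):** "Outpatient treatment will last 10 weeks and consist of thrice-weekly clinic visits".
- **Section 6.4 (dosing tables):** weeks 1 to 10 for all four conditions, with week 10 labelled as run-down.
- **Section 7.2.3:** "During the 9-week treatment phase participants will be scheduled to attend three clinic visits per week (MWF".
- **Section 7.2.5:** the end-of-study visit is at week 9.
- **Section 8 (assessment schedule):** an admit week followed by weeks 1 to 10.

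Section 1 also lists a secondary endpoint tied to the end of treatment: "abstinence rates during the last 2 weeks of treatment".

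**The concern.** The binary retention outcome asks for more weeks of treatment than any participant is offered. If nobody can meet the definition, every participant has the same value and a logistic regression has nothing to model.

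Replacing 12 with the planned duration does not settle the matter, because the protocol supports two planned durations. An analyst would have to choose between week 9 and week 10, possibly after seeing who left in the final week. The same choice affects two other analyses:

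- **Time to drop-out.** A participant who leaves in week 10 is an event if follow-up for drop-out ends at week 10, and is censored if it ends at week 9.
- **End-of-treatment abstinence.** The two-week window is weeks 8-9 or weeks 9-10.

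**Working it through.** **Step 1: compare the threshold with the schedule.** The SAP requires 12 weeks, which at three visits a week is 12 × 3 = 36 visits. The longest treatment in the protocol is 10 weeks, or 10 × 3 = 30 visits; the 9-week version has 9 × 3 = 27. Adding the admit week gives 11 weeks, still short of 12. The other 12-week duration, in section 6.2, describes a cited open-label study and not this trial.

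**Step 2: check whether Table 1 implies a longer treatment.** Table 1 in section 6.5 prints columns for weeks 11 to 13 (visits 31 to 39), so it could be the source of a 12-week figure. Its draw cells for weeks 10 to 13 are empty. Where filled, week w gives w draws at each of three visits plus a bonus of 5, that is 3w + 5:

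| Week | 1 | 2 | 3 | 4 | 5 | 6 | 7 | 8 | 9 | Sum |
|---|---|---|---|---|---|---|---|---|---|---|
| Draws | 8 | 11 | 14 | 17 | 20 | 23 | 26 | 29 | 32 | 180 |

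This reproduces the printed "Total: 180 Draws" exactly from weeks 1 to 9. On the same pattern, 10 weeks would give 180 + 35 = 215 and 12 weeks would give 294. The blank columns therefore do not describe treatment in weeks 11 or 12.

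**Step 3: consequence for the model.** With 200 participants allocated equally to four conditions, each arm has 200/4 = 50. Completers under the SAP definition number 0 of 50 in each arm. For two arms with intercept b and log odds ratio d, the log-likelihood is −50·ln(1 + e^b) − 50·ln(1 + e^(b+d)). As b decreases it approaches its upper limit of 0 for any finite d. At b = −20 it is about −1.4×10⁻⁷, −2.1×10⁻⁷ and −3.8×10⁻⁷ for d = −1, 0 and 1. No finite maximum exists, and the sample odds ratio is 0/0.

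**Step 4: is there one obvious replacement?** These places bear on whether week 10 counts:

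| Place | Points to week 9 | Points to week 10 |
|---|---|---|
| Section 1 | | 10 weeks of treatment |
| Section 6.4 | week 10 is run-down | dosing tables include week 10 |
| Section 6.5 | Table 1 draws end at week 9 | |
| Section 7.2.3 | 9-week treatment phase | |
| Section 7.2.5 | end-of-study assessments | |
| Section 8 | last computerized tests | closing BDI-2 and BSCS; Fishbowl marked |

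The draw rule in section 6.5 reads "During Treatment, for each visit attended, subjects will earn a draw from the attendance voucher", which with Table 1 suggests that week 10 is not treatment. The Fishbowl mark at week 10 is weak evidence the other way, because that row is also marked in the admit week, for which Table 1 has no draws either.

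**Step 5: how much the choice could matter.** One participant is 1/50 = 2 percentage points of an arm's completion rate. The documents give no attrition rate, so the following rests on assumptions. Suppose two arms have equal week-9 completion, and k participants leave between the two cut-offs in one arm only. The odds ratio is 1.00 at week 9. At week 10 it becomes:

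| Assumed week-9 completion | k = 1 | k = 3 | k = 5 |
|---|---|---|---|
| 40% (20/50) | 0.92 | 0.77 | 0.64 |
| 50% (25/50) | 0.92 | 0.79 | 0.67 |
| 60% (30/50) | 0.92 | 0.78 | 0.67 |

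For example, at 50% and k = 5: (20/30)/(25/25) = 0.67. For scale, an assumed constant weekly drop-out of 3% takes completion from 76.0% at week 9 to 73.7% at week 10, a loss of 2.3 points or about 1 participant in 50. At 10% it goes from 38.7% to 34.9%, a loss of 3.8 points or about 2 in 50. Five late leavers in one arm and none in the other is therefore the far end of the range.

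**The case against.** The strongest reply is that this is a wrong number in a supporting analysis. The primary outcome is the weekly proportion of days without cocaine use, and the protocol's own retention endpoint is time in study, which is secondary. The proportional hazards model addresses time in study without the 12-week rule. No analyst would run the literal definition; substituting the planned end of treatment makes the odds ratio estimable. Most of the protocol also fits a single reading: nine weeks of run-up and maintenance followed by a run-down week. Finally, the odds-ratio shifts depend on late drop-out in one arm only. Equal losses from equal arms would leave the ratio at 1.00, and even 20/50 against 25/50 has an approximate 95% interval of 0.30 to 1.47 (standard error of the log odds ratio 0.40).

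Much of this stands. The damage is confined to the completer analysis and to the analyses that share its time point, substitution does restore estimability, and the shifts are an illustration that shows no change of inference. The reply does not supply the missing definition. The nine-plus-one reading is plausible but stated nowhere, and the abstract calls all 10 weeks treatment. The SAP also points to a section B.3.2.5.ii that is not in the documents reviewed; it is cited for how cocaine use is measured, and nothing shows that it settles the retention time point.

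**Conclusion.** The concern holds. As written, one of the two planned retention analyses under H1 has 0 of 200 possible completers and gives no odds ratio. This follows directly from the documents and needs no assumption. The obvious repair leaves an unwritten choice between week 9 and week 10, worth 2 percentage points of an arm's completion rate per late leaver. Under the stated assumptions (equal week-9 completion of 40% to 60%, 1 to 5 late leavers in one arm only), the odds ratio moves from 1.00 to between 0.92 and 0.64. The primary outcome and the time-to-drop-out model remain estimable, although the latter's administrative censoring week is also unsettled. Because the faulty definition sits in the primary hypothesis section, it should be corrected before unblinding.

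**What to change.** 1. Reconcile the 9-week and 10-week statements in protocol sections 1, 6.4, 6.5, 7.2.3, 7.2.5 and 8. State whether run-down week 10 counts as treatment, and resolve the difference between Table 1 and the Fishbowl row for that week.
2. Before unblinding, replace the 12-week threshold in the SAP with the single reconciled duration, and name the visit that marks completion.
3. Use the same week to censor time to drop-out, and state the calendar weeks of the two-week abstinence window so that it follows from the same definition.

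The cost is a line or so of SAP wording and a protocol clarification. No new data or patients are needed.
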